Effect of preoperative single-dose tamsulosin on postoperative urinary retention after mid-urethral sling placement: a randomized, double-blinded, placebo-controlled trial

Principal Investigator
[name]

Clinical Research Supervisor
[name]

Sub-Investigator(s)
[name] MPH
[name]
[name]
[name]
[name] MHS
[name]

Sponsor
None

Site of Investigation
Northshore University Health System

Date of Protocol: 04/08/2023
NCT05753670

Protocol Version: 2

Purpose

The purpose of this study is to evaluate whether a single dose of preoperative tamsulosin may improve postoperative urinary retention rates determined by postoperative retro-fill voiding trial compared with placebo.

Background

Postoperative urinary retention has been defined as the inability to void despite having fluid in the bladder during the postoperative period (3). Urinary retention after pelvic reconstructive surgery requiring indwelling catheter or self-catheterization usage occurs in approximately 30-60% of patients postoperatively (1,2,3).

During a retro-fill voiding trial, the bladder is back-filled with a set amount of sterile water (often 300mL), the catheter is removed, the patient is permitted to void and the voided volume is compared with a bladder scan post void residual volume. “Passing” a voiding trial has previously been defined as voiding equal or greater than $\frac{1}{3}$ the residual volume, whereas others characterize “passing” as voiding at least 200mL and voiding a greater volume than the post-void residual volume (4). If the patient does not “pass” the voiding trial, the patient is characterized as having postoperative urinary retention and is discharged home with an indwelling catheter to prevent detrusor injury from bladder overdistention, pain and urinary tract infection (5).

Many women consider being discharged home with a Foley catheter to be a surgical complication and describe catheter use as the worst aspect of their surgery (1,6). Indwelling catheters are the leading cause of hospital-acquired urinary tract infections (UTIs), are often a source of embarrassment and inconvenience for patients, and often require additional office visits and healthcare utilization (8).

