 - a. Determine the postoperative urinary retention rates after preoperative administration of tamsulosin compared with placebo. This will be determined immediately postoperative in the postoperative recovery room based on whether patients pass or fail their voiding trial described above. The result will be documented in electronic medical records and obtained from chart review.
2. Secondary outcome measures:

- a. Determine differences in postoperative pain, hypotension, postoperative UTI after preoperative administration of tamsulosin compared with placebo. This data will be obtained by electronic data pull and chart review.
- b. Determine time to Foley catheter removal and voiding trial in the recovery area between the two study groups which will be obtained by chart review of the documentation for Foley removal.
- c. Determine the difference in unplanned admissions, office visits or Northshore encounters within 30 days after surgery after preoperative administration of tamsulosin compared with placebo. This data will be collected via chart review.
- d. Determine correlation between subjective measure of “feeling empty” and PVR. This will be documented in the electronic medical record by the postoperative nursing staff along with the PVR result obtained from ultrasound in the postoperative recovery area.

Methods

This is a prospective randomized, double-blinded, placebo- controlled trial of patients who are undergoing elective mid-urethral sling placement with or without concomitant prolapse surgery with the Center for Pelvic Health at the Northshore University Health System.

Women presenting to our tertiary urogynecology clinic with stress urinary incontinence who decide to proceed with surgical treatment of stress urinary incontinence via a mid-urethral sling placement will be invited to participate in this study. This study will be discussed with the patient by their surgeon during their clinic initial screening visit or preoperative visit based on inclusion and exclusion criteria listed below. This study will involve no additional pre-operative tests or questionnaires, beyond our routine clinical pathway for women presenting with stress urinary incontinence. Written consent will be obtained.

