After surgery, patients will then undergo a retro-fill voiding trial in the recovery area. The voiding trial will be performed as follows: using a Foley catheter placed in the OR, we will retro-fill the bladder with 300mL of sterile normal saline (using the catheter that is already in place, a trained nurse will fill the bladder with sterile normal saline), the catheter will be removed and the patient will be asked to void. The measured voided volume will be recorded and a bladder scan post-void residual (PVR) volume will be obtained. Patients will be asked if they "feel empty" as a subjective measure of voiding success. As described in prior studies, the patient will fail the voiding trial if voided volume is less than $\frac{1}{3}$ total bladder volume and PVR is greater than or equal to 200mL. Upon failing the voiding trial, the patient will be discharged home with a Foley catheter with plan for outpatient follow up for catheter removal in clinic, consistent with our current protocol. According to our current protocol, patients discharged with a Foley catheter can either remove the catheter at home in 48-72 hours after surgery or call our office to have it removed at the next available appointment within 2-5 days postoperatively.

We will then evaluate the rate of postoperative urinary retention after preoperative administration of tamsulosin compared with placebo. Any collected information will be de-identified.

The current rate of postoperative urinary retention at our institution based on chart review is 25%. Published data discussed above have described a postoperative urinary retention rate decrease of 65-88% (10-14). Based on a sample size calculation to achieve 80% power, to evaluate for a 65% decrease in our urinary retention rate (from 25% to approximately 8.8%) we will need to recruit 160 total subjects (80 per group).

Inclusion criteria

Mid-urethral sling placement (CPT 57228)

Exclusion criteria

Age <18

Planned combined cases with colorectal surgery, general surgery, or gynecology-oncology

Planned sling revision or history of prior sling placement

Known history of urinary retention

Concomitant intravesical botulinum injections

Known contraindication to tamsulosin

Variables

MRN

Age (at time of surgery)

Gravity and para

Race/ethnicity

Smoking status

Menopausal status

BMI

Comorbid conditions
 Diabetes
 Hypertension
 Other cardiovascular disease
 Respiratory disease
 Obstructive sleep apnea
 Chronic pain conditions

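### Does the undefined total bladder volume in the voiding-trial rule leave the primary endpoint unsound?

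*Combined protocol and SAP*

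**What the plan says.** Outcome measures, item 1a, sets the primary endpoint in the recovery room, "based on whether patients pass or fail their voiding trial described above". On the source it adds: "The result will be documented in electronic medical records and obtained from chart review".

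Two sets of criteria stand before that item, both in Background and both reported from the literature. In one, passing "has previously been defined as voiding equal or greater than" one third of the residual volume. In the other it is characterised "as voiding at least 200mL and voiding a greater volume than the post-void residual volume".

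The trial's own rule comes after item 1a, in Methods. Staff proceed as follows: "we will retro-fill the bladder with 300mL of sterile normal saline". Then: "The measured voided volume will be recorded and a bladder scan post-void residual (PVR) volume will be obtained". Finally, "the patient will fail the voiding trial if voided volume is less than" one third of the "total bladder volume and PVR is greater than or equal to 200mL". The term total bladder volume appears only there and is not defined.

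The Variables section lists postoperative urinary retention, the feeling-empty item and the time from voiding trial to void. It lists neither voided volume nor PVR, although outcome 2d compares feeling empty with PVR.

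**The concern.** One pass/fail result is the whole primary endpoint, so a loose definition deserves attention. Three things look loose.

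- The cross-reference in 1a points upward, to two criteria that differ from the Methods rule and from each other.
- The denominator can be read as the 300 mL fill or as void plus PVR. With a void of 110 mL and a PVR of 250 mL, the patient fails on void plus PVR (110 < 360/3 = 120) and passes on the fill (110 ≥ 300/3 = 100).
- With neither volume on the Variables list, the planned dataset would seem unable to show or correct inconsistent charting.

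If recovery staff used different denominators, identical volumes could be charted differently. Patients, clinicians and nurses are blinded, so the result would be noise shared by both arms. The stake is therefore power. The plan aims at 80% power and shows no margin.

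**Working it through.** **1. The plan's own figure.** Inputs from Methods: 25% against 25% × (1 − 0.65) = 8.75%, 80% power, 80 per group. Significance level 0.05 from Statistical Methodology, taken as two-sided. Unpooled normal formula:

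n = (1.960 + 0.842)² × (0.25 × 0.75 + 0.0875 × 0.9125) / (0.25 − 0.0875)² = 79.5, so 80 per group.

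Full binomial enumeration of the two-sided Pearson chi-squared test at 80 per group gives 80.0% power. The planned 160 is reproduced.

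**2. Where the two readings part.** Let V be the void and R the PVR, in mL.

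- Fill reading: fail if V < 100 and R ≥ 200.
- Sum reading: fail if V < (V + R)/3 and R ≥ 200, which is V < R/2 and R ≥ 200.

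A fail on the fill reading has V < 100 ≤ R/2, so it is also a fail on the sum reading. The reverse breaks only when 100 ≤ V < R/2. Then R > 2V, so V + R > 3V ≥ 300. Disagreement therefore needs a total above 300 mL, and it always runs from fail (sum) to pass (fill). Enumeration of every whole-mL pair with a total up to 1000 mL found no exception.

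| Total (mL) | Voids that change class (mL) |
|---|---|
| 300 or less | none |
| 310 | 100–103 |
| 330 | 100–109 |
| 360 | 100–119 |
| 450 | 100–149 |

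The totals above 300 mL are illustrations. The documents give no distribution of totals.

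**3. What it could cost.** Assume that a share f of patients who fail on the sum reading lies in the band in each arm, and that half of them are charted as pass. Both rates are multiplied by (1 − f/2).

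| f (assumed) | Rates | Difference (points) | Exact power |
|---|---|---|---|
| 0 | 25.0% vs 8.75% | 16.25 | 80.0% |
| 5% | 24.4% vs 8.5% | 15.8 | 78.7% |
| 10% | 23.75% vs 8.3% | 15.4 | 77.4% |
| 20% | 22.5% vs 7.9% | 14.6 | 74.7% |

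The common factor cancels in the ratio, so the relative reduction stays at 65%.

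**4. The cross-reference.** At a 300 mL total the lowest passing void is 75 mL or 200 mL under the two Background definitions, and 100 mL under Methods on either denominator. The gap would matter if a reader had to choose among the three. Background attributes its two to earlier work, and only Methods says when a patient in this trial fails. Background does describe the procedure itself (fill, catheter out, void, scan), so the upward reference is not empty.

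**5. The Variables list.** It also omits treatment group and the time of Foley removal, although outcome 2b takes the latter from the chart. The list is evidently not exhaustive. Methods has the void recorded and the PVR obtained, and outcome 2d has the PVR entered in the medical record.

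**The case for a change.** The strongest opposing case is that a sole primary endpoint should not rest on inference, and that clarity here is nearly free: one defined term, one corrected reference, two more abstracted fields. Totals above 300 mL are not excluded, because Methods does not say that the bladder is empty before filling and some interval before voiding is expected. PVR is needed for outcome 2d under any reading, so its absence from the list is a real inconsistency.

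The power table is also not the worst case. It counts lost fails only. If the fill is the intended denominator and some staff use the sum, true passes would be charted as fails, which dilutes more. With 2% of true passes miscoded in each arm, the rates become 0.25 + 0.75 × 0.02 = 26.5% and 0.0875 + 0.9125 × 0.02 = 10.6%. The relative reduction falls to 60%, and power by the pooled normal formula goes from 78.9% to 74.1%.

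The textual points stand. What does not stand is the step from an undefined term to inconsistent charting. That step needs staff who disagree about the denominator and enough patients in a narrow band, and the documents show neither. They describe one health system, a trained nurse doing the fill, and an existing discharge protocol. If staff share one convention, the definition is unstated but the data are consistent.

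Replacing the charted result with one derived from volumes is not a clear gain either. The charted result sends the patient home with or without a catheter, and Background names home catheter use as the consequence of interest. The 25% planning rate also came from chart review. A derived primary could depart from both.

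**Conclusion.** No change to the plan follows. The upward reference is a clerical slip with one sensible target, the Methods rule. The undefined denominator and the short field list are gaps in detail that the study team can fill from its own practice and from volumes it already measures. Which denominator is meant is for the investigators to state, and this review takes no view on it. Keeping the charted pass/fail as primary is a fair trade-off, and a check against the recorded volumes remains open to the analysts.

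On size, the readings cannot differ at totals up to 300 mL. Under the assumed shares of 5% to 20%, half of them miscoded, the loss is 1.3 to 5.3 points of power. The opposite miscoding at an assumed 2% costs 4.8 points. No bias between arms is expected, given the blinding in Methods. These figures rest on assumed shares, on miscoding unrelated to arm, and on a two-sided test at 0.05. The conclusion would change if there were evidence that staff chart by different denominators and that totals well above 300 mL are common. The documents contain no such evidence.

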Tamsulosin is an alpha-adrenergic receptor blocker which is thought to increase smooth muscle relaxation and improve urinary flow (9). Current literature has been primarily focused on the effect of tamsulosin in men with benign prostatic hyperplasia, however may be beneficial in women as well with limited studies for postoperative urinary retention (9). Chapman, et al published a randomized control trial evaluating postoperative urinary retention after female pelvic reconstructive surgery (10). These patients underwent 10 days of tamsulosin (3 days preoperative and 7 days postoperative) and were found to have a 65% decrease in the urinary retention rate from 25.8% to 8.8% (10). Livne, et al published a study evaluating postoperative urinary retention decrease of 79.2% after postoperative administration of dibencyline (an alpha-adrenergic receptor blocker) in women undergoing hysterectomy (post-operative urinary retention rate of 18.75% in controls and 3.9% in the treatment group) (11). Additional studies have also been published evaluating postoperative urinary retention in men and women undergoing various surgeries and have demonstrated a decrease in postoperative urinary retention after tamsulosin administration from 72-88% compared with controls (12-14). These studies vary in tamsulosin administration from multiple days preoperative and postoperative to multiple doses preoperative and postoperative to a single postoperative dose, however no studies have been published in evaluating a single preoperative dose of tamsulosin and the effect on postoperative urinary retention (10-14). This has previously been studied as tamsulosin reaches a steady state in approximately 5 days, however when tamsulosin is given in a fasting patient, it can reach the maximum blood concentration in approximately 4-5 hours (10,15). As the majority of female pelvic reconstructive surgeries performed by our department are same-day surgeries, with patients being discharged the day

of surgery, we would like to investigate the effect of a single preoperative dose of tamsulosin on postoperative urinary retention and, by effect, home catheter usage after surgery. Tamsulosin is cost-effective at approximately \$2 per tablet (16). Despite primarily being prescribed for benign prostatic hyperplasia, tamsulosin has been found to be a safe and well-tolerated treatment for voiding dysfunction in women (9).

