Postoperative urinary retention is common after pelvic reconstructive surgery with mid-urethral sling placement and is extremely bothersome to patients. Tamsulosin is a low-risk, well tolerated, cost-effective medication that studies have suggested may decrease the rate of postoperative urinary retention (9). No study to date has evaluated preoperative administration of single- dose tamsulosin for postoperative urinary retention in a randomized placebo-controlled trial.

Hypothesis

We hypothesize that providing preoperative tamsulosin will improve postoperative urinary retention rates determined by postoperative retro-fill voiding trial compared with placebo.

Objectives

The **primary objective** of this study is to evaluate whether preoperative administration of tamsulosin will decrease the rate of postoperative urinary retention after mid-urethral sling placement with or without concomitant prolapse surgery compared with placebo. The **secondary objective** of this study is to evaluate for any differences in hypotension, unplanned admission, postoperative UTI, or unplanned 30-day healthcare encounters after preoperative tamsulosin compared to placebo.

Specific Aims

1. Compare the postoperative urinary retention rates after preoperative administration of tamsulosin compared with placebo.
2. Compare differences in postoperative pain (postoperative nursing documentation performed in the recovery area based on a Likert scale of 0-10), hypotension (immediately postoperative) or postoperative UTI (UTI within 30 days of procedure) after preoperative administration of tamsulosin compared with placebo.
3. Compare time to Foley catheter removal and voiding trial in the recovery area between the two study groups.
4. Evaluate the difference in unplanned admission the day of surgery or unplanned admission within 30 days after surgery, unplanned office visits within 30 days after surgery or Northshore encounters within 30 days after surgery after preoperative administration tamsulosin compared with placebo. These medical encounters will include any need for additional medical treatment, phone calls, complications or patient concerns within 30 days postoperatively. This data will be collected via chart review.
5. Evaluate subjective measure of “feeling empty” after a void compared with PVR value.

Outcome measures

1. Primary outcome measure:

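### Current alpha-blocker use is neither named in the exclusion criteria nor listed as a variable, so any enrolled user would dilute the tamsulosin–placebo contrast unnoticed

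*Combined protocol and SAP*

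**What the plan says.** **Eligibility.** The one inclusion criterion is the sling procedure, with no condition on medication. The Exclusion criteria section has six items: age under 18, planned combined cases with certain other services, sling revision or a prior sling, "Known history of urinary retention", concomitant intravesical botulinum injection, and "Known contraindication to tamsulosin". The term contraindication is not defined. No washout or medication check is described.

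**Data.** Methods states: "This study will involve no additional pre-operative tests or questionnaires" beyond routine care. The Variables list records diagnoses, among them hypertension and "Other cardiovascular disease", as well as procedures, anaesthesia, surgeon and outcomes. It has no field for current medication. It does include the medical record number, and Outcome measures relies on electronic data pulls and chart review.

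**Rationale.** Background says of the drug's mechanism: "Tamsulosin is an alpha-adrenergic receptor blocker which is thought to increase smooth muscle relaxation and improve urinary flow". It adds that "tamsulosin has been found to be a safe and well-tolerated treatment for voiding dysfunction in women". It also reports that a different alpha-blocker, given after hysterectomy, lowered retention from 18.75% to 3.9%.

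**Objectives.** The primary objective compares retention after preoperative tamsulosin with placebo. The secondary objective is to "evaluate for any differences in hypotension, unplanned admission, postoperative UTI, or unplanned 30-day healthcare encounters after preoperative tamsulosin compared to placebo".

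**The concern.** By the protocol's own account, alpha-blockers as a class lower the risk of postoperative retention. Background also describes tamsulosin as a treatment for voiding problems in women, and recruitment is from a urogynecology clinic. A woman who takes and tolerates tamsulosin has no evident contraindication to it. A woman treated for voiding dysfunction without retention is not caught by the retention item. As written, the criteria could therefore let a current user be randomised.

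A user allocated to placebo is already exposed to the class under test. A user allocated to tamsulosin receives an extra dose on top of existing treatment, which is not the single preoperative dose that the protocol presents as its novelty. Randomisation balances users between arms in expectation but does not restore the lost contrast. The retention difference would shrink towards zero, and the hypotension comparison would be harder to interpret. Because no medication field is planned, the dataset would not show whether this had happened, and the planned multivariable models could not take it into account.

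**Working it through.** **Inputs from the protocol (Methods, Statistical Methodology).** Control rate 25%; relative reduction 65%, so active rate 0.25 × 0.35 = 8.75% (the protocol rounds to about 8.8%); 80 per group; 80% power; significance at 0.05, taken as two-sided because sidedness is not stated.

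**Reproducing the plan's figure.** With the unpooled normal approximation, n per arm = (1.960 + 0.842)² × [0.25 × 0.75 + 0.0875 × 0.9125] / (0.25 − 0.0875)² = 79.5, so 80 per arm and 160 in total. Exact enumeration of two binomials with 80 per arm and the uncorrected two-sided chi-squared test gives 80.0% power. The point does not rest on a sample-size error.

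**Input that the documents do not give.** The share q of women already using an alpha-blocker is unknown. Values of 2%, 5% and 10% are assumed, which means 80q = 1.6, 4 and 8 expected users per arm.

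**Scenario A: 25% is the rate in non-users.** Users are assumed to have the planned active rate in either arm.

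- Placebo rate = 0.25 − q × (0.25 − 0.0875) = 0.25 − 0.1625q
- Active rate = 0.0875

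**Scenario B: the 25% chart-review rate already includes users.** Users again have 8.75% in both arms, and non-users have a 65% reduction.

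- Non-user placebo rate r = (0.25 − 0.0875q) / (1 − q)
- Placebo rate = 0.25
- Active rate = (1 − q) × 0.35r + 0.0875q = 0.0875 + 0.056875q

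Power in both scenarios is by the same exact enumeration with 80 per arm:

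| q (assumed) | A: placebo rate vs active rate | A: power | B: placebo rate vs active rate | B: power |
|---|---|---|---|---|
| 0% | 25.0% vs 8.75% | 80.0% | 25.0% vs 8.75% | 80.0% |
| 2% | 24.7% vs 8.75% | 78.6% | 25.0% vs 8.9% | 79.3% |
| 5% | 24.2% vs 8.75% | 76.4% | 25.0% vs 9.0% | 78.2% |
| 10% | 23.4% vs 8.75% | 72.5% | 25.0% vs 9.3% | 76.3% |

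At 10% use, the loss is 80.0 − 72.5 = 7.5 points in A and 80.0 − 76.3 = 3.7 points in B. Scenario B therefore gives about half the loss of A.

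**Could there be no users at all?** With 160 women, the chance of none is (1 − q)^160: 0.99^160 = 20% at an assumed 1% use, and 0.995^160 = 45% at 0.5%.

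**The case against.** The strongest reply is that nothing in the documents shows that the problem occurs. No prevalence is given, and the retention exclusion may already remove some likely users. A screener could also read the contraindication item as covering concurrent use, and a clinician orders each dose. The trial compares tamsulosin with placebo in women having a sling. Randomisation keeps that comparison valid and the type I error intact, so enrolling users changes the population and may dilute the effect but does not create a false positive. All of this stands and limits the size of the point. It does not remove the gap, because an undefined item can be read differently by different surgeons, and without a field the team cannot show that use was zero.

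A reader might infer more than the documents support:

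- *That some placebo patients are in fact alpha-blocked.* This is only a possibility; the number could be zero.
- *That women with hypertension bring alpha-blocker use with them.* Hypertension is a recorded comorbidity, but the documents do not link it to alpha-blockers.
- *That exposed women could never be identified.* The medical record number and chart review are in the plan, so the information is unplanned rather than lost.
- *That there is a demonstrated safety harm from double exposure.* No figure or statement in the documents supports one. What can be said is that the hypotension comparison becomes less clear.

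**Conclusion.** The point holds as a minor one, a cheap improvement. Current alpha-blocker use is not named in the exclusions, is not clearly covered by the contraindication item, and is not among the variables, although the protocol's own rationale makes it relevant to the primary outcome. The expected direction is towards no difference, not in favour of tamsulosin.

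For an assumed 2% to 10% use, the power loss is 1.4 to 7.5 points if the 25% control rate describes non-users, and 0.7 to 3.7 points if that rate already includes them. The documents do not say which applies. Both ranges assume that every user has the full planned active-arm rate in either arm. Women treated for voiding dysfunction may have a different underlying risk, which the documents do not give. If use is rare, the numerical effect is small.

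**What to change.** 1. State in the Exclusion criteria that women currently using tamsulosin or another alpha-blocker are not eligible. The clinical details, including any look-back period, are for the investigators to decide.
2. Add to the Variables list: alpha-blocker use at baseline (yes/no, drug), taken from the chart as it stood before the trial medication was given.
3. For women already enrolled, extract this field by chart review. Keep the primary comparison in all randomised women and report it again without users as a sensitivity analysis. With one or two users per arm this will say little about the effect in users, but it will document the extent of exposure.

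The cost is one eligibility line and one chart-review field, with no extra test or visit. The downside is that the few users are not enrolled and the result does not apply to them.

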Prior hysterectomy
Prior abdominal surgery
History of prior prolapse surgery
Prolapse stage
Location of surgery (Highland Park Hospital, Evanston)
Type of anesthesia
ASA grade
Incontinence procedure
Mid-urethral sling placement: CPT 57228
Concomitant prolapse procedures
 Anterior colporrhaphy: CPT 57240
 Posterior colporrhaphy: CPT 57250
 Combined anterior and posterior colporrhaphy: CPT 57265
 Apical prolapse suspension
 Vaginal vault suspension
 Intraperitoneal: CPT 57283
 Extraperitoneal: CPT 57282
 Sacrocolpopexy: Minimally invasive (robotic-assisted and laparoscopic): CPT 57425

Concomitant procedures
 Hysterectomy
 Rectopexy

Intraoperative complications
Additional procedures (lysis of adhesions)

Intraoperative consultations

Length of procedure

Estimated blood loss

Surgeon
 Surgeon experience (< 5 years, > 5 years)

Total time in PACU

Time of day in ASU

Total time in ASU

Immediate postoperative complications
 Uncontrolled nausea
 Uncontrolled pain
 Hypotension
 Incisional bleeding

Postoperative pain scores upon admission to the ASU

Postoperative pain scores at discharge

Reason for postoperative admission (surgeon choice, comorbid conditions, nausea/vomiting, etc.)

Time from voiding trial to void

Subjective determination of “feeling empty”

Postoperative urinary retention

Postoperative urinary tract infection (UTI)

Unanticipated healthcare encounters

Urogynecology office visit (excluding voiding trial(s))

ED visit

Readmission within 30 days of discharge

Unplanned phone calls

Complications 30 days after discharge

Urinary tract infection

Reoperation

Venous thrombotic event

Statistical Methodology

A statistician from the NorthShore Research Institute will assist with statistical analysis. Data will be analyzed using SAS 9.4 (SAS Inc., Cary, NC). Demographic and clinical characteristics between groups will be compared using Student t-test (parametric) or Mann-Whitney U test (nonparametric) for continuous variables and Chi-squared test or Fisher exact test for categorical variables. Multivariable logistic regression models will be constructed to examine the relationship of an outcome with demographic and clinical covariates. Statistical significance will be defined at p-value < 0.05.

Literature review

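### Does the Statistical Methodology section leave the primary comparison of retention rates, and its 80% power, undetermined?

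*Combined protocol and SAP*

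**What the plan says.** The primary outcome is binary, pass or fail on the voiding trial. Outcome measures gives the comparison as "Determine the postoperative urinary retention rates after preoperative administration of tamsulosin compared with placebo", and Methods repeats it: "We will then evaluate the rate of postoperative urinary retention after preoperative administration of tamsulosin compared with placebo". The same part of Methods gives the sample size: "Based on a sample size calculation to achieve 80% power, to evaluate for a 65% decrease in our urinary retention rate", from 25% to about 8.8%, with 80 patients per group.

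The Statistical Methodology section is short. Its sentence on tests opens "Demographic and clinical characteristics between groups will be compared using Student t-test (parametric", adds Mann-Whitney as the non-parametric alternative, and ends with "Chi-squared test or Fisher exact test for categorical variables". Next comes the modelling sentence: "Multivariable logistic regression models will be constructed to examine the relationship of an outcome with demographic and clinical covariates". The last sentence is "Statistical significance will be defined at p-value < 0.05", with no statement on one- or two-sided testing.

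**The concern.** Read literally, the sentence on tests covers patient characteristics, so the primary outcome has no test of its own. If the sentence is stretched to cover retention, two tests remain with no rule for choosing between them, and they do not behave alike at 80 per arm. A borderline result could be significant by one and not by the other, and the claimed 80% power would hold under only one.

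Two further points add to the unease. No effect estimate or interval is planned, so a non-significant p-value might be misread as evidence of no effect. The logistic model is also loosely described, and the Variables list contains items recorded after dosing, such as blood loss, recovery-area times and pain scores. A treatment effect taken from a model that included those could be biased. At stake would be the credibility of the main result if the choices were made after unblinding.

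**Working it through.** **Inputs.** Control rate 25%, treated rate 8.75% (a 65% reduction: 0.25 × 0.35 = 0.0875; the protocol rounds to 8.8%), 80 per arm and 80% power, all from Methods. Alpha 0.05 is from Statistical Methodology. Two-sided testing is an assumption.

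**1. Reproduce the 160.** Uncorrected formula, unpooled variance:

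n per arm = (1.960 + 0.842)² × [p₁(1 − p₁) + p₂(1 − p₂)] / (p₁ − p₂)², where the squared term is 7.849 before rounding.

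- At 8.75%: 7.849 × (0.1875 + 0.0798) / 0.1625² = 79.5
- At 8.8%: 7.849 × (0.1875 + 0.0803) / 0.162² = 80.1

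This matches 80 per arm. Other versions fit less well: pooled variance gives 83, the two-sided continuity correction 95, and one-sided 0.05 without correction 65 or 66. The sample size therefore points to an unadjusted, uncorrected, two-sided comparison of two proportions.

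**2. Exact power at 80 per arm.** Enumerating all 81 × 81 possible outcomes, two-sided 0.05:

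| Test | 25% vs 8.75% | 25% vs 8.8% |
|---|---|---|
| Chi-squared, uncorrected | 80.0% | 79.7% |
| Fisher exact | 74.1% | 73.8% |
| Chi-squared, continuity-corrected | 73.3% | 73.0% |

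At 8.75%, uncorrected chi-squared is significant and Fisher is not in 5.8% of trials; the reverse never occurs. For example, 20 versus 10 retentions gives p = 0.043 and p = 0.067.

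**3. Which test would be used?** By common convention Fisher replaces chi-squared when an expected cell count falls below 5. With equal arms, the smallest expected count is half the total number of retentions. At the planning rates that is 80 × (0.25 + 0.088) / 2 = 13.5. A count below 5 needs fewer than 10 retentions in all, which has probability of about 0.001%. Applying the convention outcome by outcome gives 79.97% power at 8.75%, the same as chi-squared throughout. In the 20 versus 10 example the expected count is 15, so chi-squared applies.

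**4. Effect size and interval.** These need only the counts. For 20/80 versus 12/80 the risk difference is 0.25 − 0.15 = 0.10, with standard error √(0.25 × 0.75/80 + 0.15 × 0.85/80) = 0.0627. The 95% CI is 0.10 ± 1.96 × 0.0627, or −0.023 to 0.223, and chi-squared p = 0.11. The interval still contains the planned 16-point difference, which a report of this result would need to show. No decision made in advance is required to compute it.

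**5. The model sentence.** It relates an outcome to patient covariates and does not mention study arm. The natural reading is a risk-factor analysis alongside the primary comparison. Nothing makes it the primary analysis, and nothing makes the Variables list its covariate set.

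**The case for a change.** The strongest contrary argument is that the primary analysis of a confirmatory trial should be written down, however obvious it seems. The expected-count rule is a convention that the protocol does not state. A statistician's later help is not the same as pre-specification. With the planned effect, about 1 trial in 17 (5.8%) would give different verdicts under the two listed tests. A few sentences would close the gap at no cost to conduct or sample size.

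Much of this stands as a remark on drafting: the section is incomplete, and naming the test, its sidedness, the risk difference with interval and the supporting role of the models would be tidier. It does not show that the plan is wrong. The 5.8% matters only if the test is picked after both results are seen, and the 74% arises only if the team departs both from usual practice and from the formula behind its own sample size. Harm from overfitting or from covariates recorded after dosing needs a treatment-effect model that the text does not describe, with a covariate set it does not give. Any figure for that harm would rest on invented inputs.

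**Conclusion.** The gap is real, but it is one of detail. The intended primary analysis can be recovered from the stated outcome, the stated comparison and the sample size: an unadjusted two-sided comparison of the proportions failing the voiding trial. Uncorrected chi-squared delivers 79.7% to 80.0% power against the stated 80%, and the usual rule for choosing between the listed tests leads to it in more than 99.99% of trials at the planning rates. Writing this down would record the expected analysis and would not replace a mistaken one, so no change is called for.

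The conclusion assumes two-sided testing at 0.05, 80 per arm, rates near the planning values, and an analyst who follows the usual expected-count convention. Had Fisher been the intended test, power would be about 74%, and about 91 or 92 per arm would be needed for 80%, but nothing in the documents points that way.
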